3.4.2. Potential Safety Issues with Laquinimod

3.4.2.1. Pregnancy

Studies in rats have shown reproductive toxicity including teratogenicity (urogenital malformations) at doses similar to the clinical dose of 0.6 mg/day in humans. Delay in puberty and reduced fertility were noted in rat offspring exposed to laquinimod in *utero* at doses higher than the clinical dose of 0.6 mg/day in humans (Section 3.2.3). The relevance to humans of these findings is not known, but cannot be excluded.

To prevent such exposure, women of childbearing potential (for example women who are not postmenopausal or surgically sterilized) must practice an acceptable method of birth control (Section 5.3) for 30 days before taking the study treatment, and two acceptable methods of birth control throughout treatment duration and until 30 days after the last dose of study medication. Acceptable methods of birth control include: intrauterine devices, barrier method (condom or diaphragm with spermicide) and hormonal methods of birth control (eg, oral contraceptive, contraceptive patch and long-acting injectable contraceptive).. Use of acceptable contraception will be ascertained at every study visit.

In addition, regular pregnancy testing is required during the study. If pregnancy is suspected despite all recommended precautions (e.g., positive urine beta-human chorionic gonadotropin [β -hCG] test result, delay of menstruation or any other reason suggesting pregnancy), treatment should be discontinued immediately. The subject should be reminded of the potential risk to the fetus, and all options, including termination of pregnancy, should be discussed.

All subjects should be counseled by the investigator about the potential teratogenicity and delayed risks for a child exposed in uterus to laquinimod and the need to use acceptable contraception and avoid pregnancy throughout treatment with laquinimod and for 30 days after the last dose of treatment was administered.

3.4.2.2. Cancer

The 2-year carcinogenicity studies in rats demonstrated an increase in uterine and oral cancers (see Section 3.2.3). It is the Sponsor's position that these findings are likely related to species-specific mechanisms, regardless, a relevance of these cancers to humans cannot be definitively excluded. Available phase 3 and extension clinical trial data show no association of laquinimod 0.6 mg/day with an increased risk of cancer.

3.4.2.3. Cardiotoxicity and Systemic Inflammation

In clinical studies performed with laquinimod's predecessor molecule, roquinimex, pericarditis/pleuritis and ischemic heart disorders were identified as important safety concerns. Serious toxicities that occurred during Phase 3 trials led to discontinuation of these trials. Roquinimex demonstrated serious toxicities including increased rates of myocardial infarction, pericarditis, and pleuritis that were observed in three Phase 3, placebo-controlled studies in MS patients. The mechanism by which roquinimex caused these events was not identified, but they were considered to be possible manifestations of a systemic inflammatory response, an assessment which was also supported by roquinimex nonclinical findings. A thorough analysis was done on the laquinimod safety data (which is mostly reflective of the 0.6 mg/day dose) to evaluate similar potential safety issues. Based on 2347 patients exposed to laquinimod 0.6 mg for over 10000 patient-years. as well as the patients exposed to 0.6 mg in the CONCERTO and ARPEGGIO studies, analyses showed that these safety issues do not constitute a clear signal for laquinimod in doses up to 0.6 mg/day. However, at doses of 1.2 and 1.5 mg, laquinimod manifested clinical evidence of myocardial infarction.

3.5. Rationale For Study Design And Dosages

3.5.1. Study Design Rationale

This double-blind active extension study makes laquinimod available to subjects who successfully completed the double-blind placebo-controlled LAQ/5062, and enables the exploration of the long term safety, tolerability and clinical effect parameters during the disease.

LAQ/5062 study results analysis demonstrated that the 0.6 mg dose of laquinimod reached its primary endpoint, namely, reduction in the cumulative number of enhancing lesions.

Accordingly, the open-label phase makes laquinimod 0.6 mg available to subjects who have completed the Termination visit of LAQ/5063 active double-blind phase (completion of the full 36 weeks or as requested by the Sponsor), and enables the exploration of the long-term safety, tolerability and clinical effect parameters during the disease.

3.5.2. Study Drug Dose Rationale

The doses of 0.3 mg and 0.6 mg laquinimod per day that were chosen for the placebo-controlled protocol LAQ/5062 will be used in the active extension study.

Laquinimod has shown to have biological activity in animal models, PK studies, four phase I studies and two phase II clinical studies. The results of the phase II study demonstrated that administration of laquinimod (0.3 mg/day) to subjects with RRMS results in decreased numbers of active lesions in the brain.

Considering that the beneficial effects of laquinimod, as demonstrated in animal models and in the phase II study, are dose-dependent, this led to the assumption that a higher dose than that used in the phase II study may lead to increased efficacy, and strongly supports investigation of a higher but safe and tolerable dose. The core study, LAQ/5062 was designed to investigate 0.3 mg, as well as, 0.6 mg. The open-label safety clinical trial of laquinimod (0.9 mg/day) in RRMS patients has shown a reasonable safety profile. Therefore, it was decided to continue exploration of laquinimod doses of 0.3 mg and 0.6 mg in this extension study.

The data from the core LAQ/5062 study showed that oral formulation of laquinimod administered in a daily dose of 0.6 mg significantly reduced the mean cumulative number of Gd-enhancing lesions as compared to placebo. The 0.6 mg dose was well tolerated, and had a safety profile that was comparable to that of the 0.3 mg dose. Based on these positive results, all subjects participating in the open-label phase will receive *laquinimod tablets* (switched to capsules upon approval of Amendment # 4) in a daily dose of 0.6 mg.

4. STUDY OBJECTIVES

- To make treatment with laquinimod available to all subjects who previously participated in LAQ/5062 study and those who completed the Termination visit of LAQ/5063 active double-blind phase (completion of the full 36 weeks or as requested by the Sponsor).
- To assess the long-term safety, and tolerability in the group that received active treatment in LAQ/5062 protocol and additional short term safety and tolerability in the group who received placebo treatment. LAQ/5063 OL phase will assess long-term safety and tolerability of 0.6 mg laquinimod once daily.

Further efficacy data will be obtained by comparing baseline to termination in the group who received placebo treatment in LAQ/5062 core study protocol.

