4.1.3. Efficacy

- Relapse Rate
- The proportion of relapse free subjects
- Number of enhancing lesions on T₁-weighted images
- Number of new T₂ lesions
- Volume of T₂ lesions

- Number of new hypointense T₁ lesion
- EDSS Score

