11.4. Efficacy Assessment

11.4.1. Number of enhancing lesions on T₁-weighted images taken on Week 36

Descriptive statistics of the number of enhancing lesions on T₁-weighted images taken on Week 36 and change from LAQ/5062 baseline and LAQ/5063 baseline to Week 36 will be presented by treatment group.

11.4.2. The number of new T₂ lesions on scan taken on Week 36

Descriptive statistics of new T₂ lesions measured on Week 36, with reference to the previous visit performed under LAQ/5062 protocol, will be presented by treatment group.

11.4.3. The volume of T₂ lesions on scan taken on Week 36

This endpoint will be analyzed using the same methodology outlined for the number of enhancing lesions on T₁-weighted images taken on Week 36 (see Section [11.4.1](#)).

11.4.4. The number of new hypointense lesions on enhanced T₁ scans taken on Week 36

Descriptive statistics of the number of new hypointense lesions on enhanced T₁ scans taken on Week 36, with reference to the previous visit performed under LAQ/5062 protocol will be presented by treatment group.

11.4.5. The proportion of subjects with no enhancing lesions on Week 36

The counts and percentages of subjects with no enhancing lesions on Week 36 will be presented by treatment group.

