11.4.6. The total number of confirmed relapses

Descriptive statistics of the total number of confirmed relapses will be presented by treatment group.

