11.4.7. The proportion of relapse-free subjects

A subject that did not experience any relapse during the treatment period will be considered as a responder for the purpose of this analysis.

The counts and percentages of relapse-free subjects will be presented by treatment group.

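### The promised before-after efficacy comparison in prior-placebo subjects is undefined for the two relapse outcomes and incomplete for the two new-lesion counts

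*Combined protocol and SAP*

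**What the plan says.** The efficacy aim in Section 4 (repeated in the Synopsis) is a single sentence: "Further efficacy data will be obtained by comparing baseline to termination in the group who received placebo treatment in LAQ/5062 core study protocol". Section 4.1.3 then lists seven efficacy outcomes. Section 11.4 treats them in three ways.

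- **Change from baseline planned.** For enhancing T1 lesions, "change from LAQ/5062 baseline and LAQ/5063 baseline to Week 36 will be presented by treatment group" (11.4.1). T2 volume follows the same method (11.4.3). EDSS gets a categorical change from baseline and from the LAQ/5062 baseline (11.4.9).
- **Count against the core-study scan.** New T2 lesions are "lesions measured on Week 36, with reference to the previous visit performed under LAQ/5062 protocol" (11.4.2). New hypointense T1 lesions are handled the same way (11.4.4).
- **On-drug period only.** For relapses: "Descriptive statistics of the total number of confirmed relapses will be presented by treatment group" (11.4.6). For relapse-free status: "A subject that did not experience any relapse during the treatment period will be considered as a responder" (11.4.7).

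Section 4.1.3 lists a relapse rate, whereas 11.4.6 reports a total number. Sections 7.1 and 7.3.3 allow the 36-week double-blind phase to end earlier at the sponsor's request; subjects still in it when Amendment 2 was approved were called in for termination.

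**The concern.** The objective asks what happened when subjects moved from placebo to laquinimod. A relapse total or a new-lesion count taken only on laquinimod cannot answer that. Such counts start at zero and can only rise, so one period's figure shows accumulation and says nothing about whether activity fell. A second period is needed for comparison, and the plan does not name one.

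The natural reference is the same subjects' own placebo period in LAQ/5062, which had the same planned length. The plan already refers back to the core study for enhancing lesions, T2 volume, EDSS, laboratory data, ECG and vital signs (11.4.1, 11.4.3, 11.4.9, 11.5.2 to 11.5.4). The outcomes that accumulate over time are the ones left without a core-period figure.

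If totals are reported and some subjects stopped early, shorter exposure by itself lowers the relapse total and raises the relapse-free share. A reader could take either as a drug effect.

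**Working it through.** The plan gives no sample size, power or precision figure to reproduce, so the check is a matching exercise followed by illustrative arithmetic.

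**1. Match the outcomes in 4.1.3 to the analyses in 11.4.**

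| Outcome | Planned analysis | Before-after contrast |
|---|---|---|
| Enhancing T1 lesions | Change from both baselines | Yes |
| T2 volume | Same method | Yes |
| EDSS | Categorical change | Yes |
| New T2 lesions | Week 36 count against core scan | Partial: two scans compared, no placebo count |
| New hypointense T1 lesions | Same | Partial |
| Relapse rate | Total number on drug | None |
| Relapse-free share | Percentage on drug | None |

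Result: three complete, two incomplete, two undefined.

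**2. Number of prior-placebo subjects.** Section 11.2 gives 2:2:1:1 and Section 11.1 expects fewer than 264. Ceiling: 264 × 2/6 = 88, or 44 per dose.

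**3. Effect of unequal exposure, assuming no drug effect.** Expected relapse total relative to the 36-week core period = weeks on extension ÷ 36. At assumed lengths of 12 and 24 weeks: 12/36 = 0.33 and 24/36 = 0.67. With an assumed constant 0.5 relapses per year (Poisson), the expected relapse-free share is exp(−0.5 × weeks/52): 71% at 36 weeks, 79% at 24 and 89% at 12. A paired table setting 36 weeks of placebo against a shortened extension would therefore favour laquinimod with no true effect.

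**4. Effect of look-back length for new lesions, assuming no drug effect.** Section 8.1.1 lists new-lesion counts among the parameters read at the baseline and Week 36 MRIs, so a placebo-period count may exist. Its look-back is not stated. Ratio of the 36-week extension count to the baseline count = 36 ÷ look-back weeks:

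| Assumed look-back (weeks) | 4 | 8 | 12 | 24 | 36 |
|---|---|---|---|---|---|
| Ratio | 9.0 | 4.5 | 3.0 | 1.5 | 1.0 |

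The comparison is interpretable only per unit time or with matched look-backs.

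**5. Precision of a relapse rate ratio (illustration).** Follow-up per period: 88 × 36/52 = 60.9 patient-years. At an assumed 0.5 relapses per year this gives 60.9 × 0.5 ≈ 30 relapses per period. Ignoring within-subject correlation, the 95% factor is exp(1.96 × √(1/30 + 1/30)) = 1.66. Halving the subjects (44) or the rate (0.25) gives about 15 relapses and exp(1.96 × √(2/15)) = 2.05. Doubling the rate to 1.0 gives about 61 relapses and exp(1.96 × √(2/61)) = 1.43.

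With a 23% reduction, the ALLEGRO figure in Section 3.3.2, 30 relapses become about 23. The ratio is 23/30 = 0.77, with 95% interval 0.77 ×/÷ exp(1.96 × √(1/30 + 1/23)), about 0.45 to 1.32.

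**The case against.** The strongest reply has four parts.

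- **New lesions.** A lesion counted as new at Week 36 against the core termination scan is, by definition, the result of comparing baseline with termination. This stands: for these two outcomes only the placebo-period count is missing.
- **Scope of the objective.** Section 4 speaks of further efficacy data and does not say every outcome must be analysed before and after. Section 11 declares the analyses exploratory and the Synopsis promises summary statistics. This lowers the consequence. It does not remove the mismatch, because no other efficacy comparison is stated and the plan does not say which outcomes it covers.
- **Value of the added contrast.** It would be imprecise, open to time trend and regression to the mean, and defined late: Section 3.5.1 already reports the LAQ/5062 result, and Appendix 8 places the study in its open-label phase. All of this stands and belongs in the labelling.
- **Feasibility.** The LAQ/5062 protocol is not part of these documents, so its scan schedule is unknown. This stands for new lesions and makes that part of the fix conditional.

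A reader might infer that the comparison cannot be made at all for four of seven outcomes, or that the clinical outcomes have no reference. The documents support neither. A reference period can be built for relapses, Section 8.1.1 has new lesions read on the baseline scan too, EDSS is a clinical outcome with a planned change, and relapse summaries are at least set side by side by treatment group.

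**Conclusion.** The point holds as a mismatch between objective and analysis. For the two relapse outcomes the comparison promised in Section 4 is undefined. For the two new-lesion outcomes it is incomplete, since the plan as written cannot show whether lesion formation changed after the switch. The other three outcomes are adequately covered. Separately, reporting relapse totals where a rate is listed mixes unequal exposure if the double-blind phase was cut short.

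The consequence is limited because everything is exploratory, so this is a low-cost improvement and not a threat to the study's safety aims. It would be too strong to say that the efficacy objective goes unanswered for most outcomes.

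The factor of 1.66 is illustrative. It rests on the ceiling of 88 subjects, an assumed 0.5 relapses per year, full 36-week follow-up in both periods and no within-subject correlation. Fewer subjects, a lower rate or shorter follow-up widen it. How far the exposure problem bites depends on how many subjects stopped early, which the documents do not give.

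**What to change.** In Section 11.4, for subjects who received placebo in LAQ/5062:

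1. **Relapses.** Report relapses per patient-year in the LAQ/5063 double-blind period against the same subjects' LAQ/5062 placebo period. Give a within-subject rate ratio with 95% CI, from a Poisson or negative binomial model with subject as the repeated unit and log follow-up time as offset.
2. **Relapse-free status.** Use a paired table over equal-length intervals only, truncating each subject's core interval to the length of that subject's extension follow-up, and state which part of the core interval is kept.
3. **New T2 and new hypointense T1 lesions.** Name the look-back scan for the placebo-period count, and compare per unit time or with matched look-back lengths. If the core scans do not allow this, say so and present the Week 36 count without a before-after claim.
4. **Enhancing lesions, T2 volume, EDSS.** Keep the planned change from baseline.
5. **Labelling.** State that the contrast is exploratory, defined after the LAQ/5062 results were known, and uncontrolled for time trend and regression to the mean.

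The cost is plan wording and a merge with core-study data, which Section 9.2 makes simple because the subject number is retained. Relapses need no new visits. That the core relapse data are held in usable form is an assumption, though a reasonable one given how often the plan already refers back to LAQ/5062. The new-lesion part depends on the core scan schedule. The downside is one more imprecise before-after estimate, which the label addresses.

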4.1. Safety And Tolerability

4.1.1. Safety

- Adverse Events (AEs)
- Physical examinations
- Vital signs and electrocardiogram (ECG)
- Clinical laboratory parameters

4.1.2. Tolerability

- Number and percentage of subjects who prematurely discontinued from the study
- Number and percentage of subjects who prematurely discontinued from the study due to AEs

4.1.3. Efficacy

- Relapse Rate
- The proportion of relapse free subjects
- Number of enhancing lesions on T₁-weighted images
- Number of new T₂ lesions
- Volume of T₂ lesions

- Number of new hypointense T₁ lesion
- EDSS Score

4.1.4. Ancillary Studies

PK assessments and population pharmacokinetics (PPK) evaluation.

5. STUDY DESIGN

5.1. Overview and Plan

This is a multinational, multicenter, randomized, double-blind, parallel-group active extension of LAQ/5062 study, assessing the tolerability, safety and efficacy of two doses (0.3 mg and 0.6 mg) of laquinimod, orally administered, in RRMS subjects, followed by an open-label phase of laquinimod 0.6 mg daily (LAQ/5063 OL).

For the double-blind phase seven planned study visits or until the Sponsor's request (see Study Task Flow Sheet, [Table 5](#)) will be conducted at Baseline (Week 0 / Termination (Week 36) of Core Study LAQ/5062), Week 4, Week 8, Week 12, Week 16, Week 24 and Week 36. For the open-label phase the following study visits (see Study Task Flow Sheet, [Table 6](#) and [Table 7](#)) will be conducted at Baseline (Month 0) / Termination visit of LAQ/5063 active double-blind phase (completion of the full 36 weeks or as requested by the Sponsor), Month 1, Month 2, Month 3, Month 6, Month 9, Month 12, Month 15, Month 18, Month 21 and Month 24. Additional visits during the further extension of the study will be at Months 30, 36, 42, 48, 54, 60 and every 6 months thereafter, until termination (as long as the Sponsor continues the development of laquinimod 0.6 mg for RRMS) or early discontinuation.

Subjects previously treated with placebo in the LAQ/5062 study will be equally randomized to one of the two active treatment groups:

- 0.6 mg of laquinimod per os (p.o.) once daily
- 0.3 mg of laquinimod p.o. once daily

Subjects previously treated with laquinimod 0.6 mg or laquinimod 0.3 mg will continue on their original treatment assignment. Once Termination visit of LAQ/5063 active double-blind phase (completion of the full 36 weeks or as requested by the Sponsor) is performed, all subjects will continue on 0.6 mg daily.

Subjects will undergo MRI scans at Baseline (Week 0 / Termination (Week 36) of Core Study LAQ/5062), and Week 36 (Termination visit of LAQ/5063 active double-blind phase [completion of the full 36 weeks or as requested by the Sponsor]). For the open-label phase MRI will be performed at baseline (Month 0 / Termination visit of LAQ/5063 active double-blind phase (completion of the full 36 weeks or as requested by the Sponsor), Month 12 and Month 24. Subjects who performed the MRI scan within the past 14 days as part of the Termination visit of LAQ/5063 active double-blind phase (completion of the full 36 weeks or as requested by the Sponsor), will not need to undergo another MRI scan for baseline visit of LAQ/5063 OL.

Subjects who discontinue treatment for any reason will continue follow-up according to scheduled visits.

Unscheduled visits may be conducted whenever required due to various reasons, for example, AEs, or possible exacerbation.

Figure 1: Treatment Groups in MS-LAQ/5062 (Core Study) and the Double-Blind and Open-Label Phases of LAQ/5063 (Extension Study)

[figure not shown]

[figure not shown]
[figure not shown]
Figure 2: Study Flowchart for MS-LAQ/5062 Core Study

Figure 3: Study Flowchart for Open-Label Phase of LAQ/5063 Extension Study

5.2. Number of Subjects

Subjects who successfully completed the LAQ/5062 study and wished to continue to the extension study (approximately 264 subjects).

Subjects who completed LAQ/5063 phase double-blind phase (completion of the full 36 weeks or as requested by the Sponsor), will be invited to continue to the open-label phase (LAQ/5063 OL).

5.3. Inclusion Criteria

Subjects must meet all inclusion criteria in order to be eligible for Study 5063:

1. Subjects must have completed 36 weeks of treatment in the LAQ/5062 study and all termination visit activities in accordance with the protocol.
2. Women of child-bearing potential (for example women who are not postmenopausal or surgically sterilized) must practice two acceptable methods of birth control for the duration of the study and until 30 days after the last dose of study medication [acceptable methods of birth control in this open label extension phase include: intrauterine devices, barrier methods (condom or diaphragm with spermicide), and hormonal methods of birth control (e.g. oral contraceptive, contraceptive patch, and long-acting injectable contraceptive)].
3. Subjects must be willing and able to comply with the protocol requirements for the duration of the study.
4. Subjects must give signed, written informed consent prior to entering this extension study.

Inclusion Criteria For The Open-Label Phase

1. Subjects must have completed the 36 weeks of treatment (completion of the full 36 weeks or as requested by the Sponsor), of the active double-blind phase.
2. Women of child-bearing potential (for example women who are not postmenopausal or surgically sterilized) must practice two acceptable methods of birth control for the duration of the study and until 30 days after the last dose of study medication [acceptable methods of birth control in this open label extension phase include: intrauterine devices, barrier methods (condom or diaphragm with spermicide), and hormonal methods of birth control (e.g. oral contraceptive, contraceptive patch, and long-acting injectable contraceptive)].
3. Subjects must be willing and able to comply with the protocol requirements for the duration of the open-label phase (LAQ/5063 OL).
4. Subjects must give signed, written informed consent prior to entering the open-label phase (LAQ/5063 OL).

Inclusion Criteria for the LAQ/5063 OL open-label phase - further extension (after visit Month 24)

1. Subjects must have completed the 24 months of treatment of the first period of the open label phase
2. Women of child-bearing potential (for example women who are not postmenopausal or surgically sterilized) must practice two acceptable methods of birth control for the duration of the study and until 30 days after the last dose of study medication [acceptable methods of birth control in this open label extension phase include: intrauterine devices, barrier methods (condom or diaphragm with spermicide), and hormonal methods of birth control (e.g. oral contraceptive, contraceptive patch, and long-acting injectable contraceptive)].

